5 STUDY POPULATION

Approximately 510 subjects (170 in each treatment group) are planned to be randomized.

5.1 Inclusion Criteria

Male and female subjects will be considered eligible for participation in the study if all the following inclusion criteria are satisfied at Visit 1 (Screening).

1. Subjects 18 to 65 years of age, inclusive.
2. An established diagnosis per McDonald Criteria ([Polman et al 2011](#)) of MS (either RR or SP course) that manifests a documented history of spasticity for at least 6 months prior to screening.
3. Spasticity due to MS as shown by a TNmAS-MAL score $\geq 2^1$ (Appendix 1).
4. Expanded Disability Status Scale (EDSS) score ≥ 3.0 (Appendix 2).
5. If receiving disease-modifying medications (eg, interferons approved for MS, glatiramer acetate, natalizumab, fingolimod, or mitoxantrone), there must be no change in dose for at least 3 months prior to Visit 1 (Screening), and the subject must be willing to maintain this treatment dose for the duration of the study. If receiving AMPYRA[®] (dalfampridine, fampridine, 4-amino puridine), subject must be at a stable dose for at least 3 months prior to Visit 1 (Screening).
6. Stable regimen for at least 3 months prior to Visit 2 (Baseline) for all medications and non-pharmacological therapies that are intended to alleviate spasticity.
 - a. Subjects taking medications indicated for the treatment of spasticity (eg, baclofen, benzodiazepines, cannabinoids, carisoprodol, dantrolene, tizanidine, cyclobenzaprine,

¹ Total numerical score of a limb accounts for the sum of the 3 main joint muscular group scores.

- any neuroleptic, ropinoprole, tolperisone, and clonidine) at Visit 1 (Screening) must wash out from these medications for at most 21 days by Visit 2 (Baseline) in order to be eligible for randomization (see [Section 7.7](#) for washout periods for specific medications). Subjects found not to meet this criterion will be withdrawn from the study and will be considered screen failures.
7. Absence of infections, peripheral vascular disease, painful contractures, advanced arthritis, or other conditions that hinder evaluation of joint movement.
 8. Creatinine clearance, as calculated by the glomerular filtration rate (GFR) using the Modification of Diet in Renal Disease Study (MDRD) formula,² of >50 mL/minute.
 9. Use of a medically highly effective form of birth control (see [Section 7.8](#)) during the study and for 3 months thereafter for women of child-bearing potential (including female subjects and female partners of non-sterile male subjects). Use of a medically highly effective form of birth control (see [Section 7.8](#)) during the study and for 3 months thereafter for any subject whose partner is not sterilized or post menopausal.
 10. Willing to sign the informed consent form (ICF).

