5.2 Exclusion Criteria

Subjects who meet any of the following criteria will not qualify for the study.

1. Any concomitant disease or disorder that has symptoms of spasticity or that may influence the subject's level of spasticity.
2. Inability to rate their level of spasticity or distinguish it from other MS symptoms.
3. Acute MS exacerbation/relapse requiring treatment or disease modifying drug dose alteration within 3 months of Visit 1 (Screening).
4. Use of high dose (120 mg daily) oral or intravenous methylprednisolone, or equivalent, within 3 months before Visit 1 (Screening).
5. Concomitant use of medications that would potentially interfere with the actions of the study medication or outcome variables (Appendix 6).
6. Use of botulinum toxin A or B for spasticity within 6 months of Visit 1 (Screening).

² GFR Calculator:

$GFR (mL/min/1.73 m^2) = 175 \times (Scr (mg/dL))^{-1.154} \times (Age (years))^{-0.203} \times (0.742 \text{ if female}) \times (1.212 \text{ if African American})$ (conventional units)

$GFR (mL/min/1.73 m^2) = 175 \times (Scr (\mu mol/L)/88.4)^{-1.154} \times (Age (years))^{-0.203} \times (0.742 \text{ if female}) \times (1.212 \text{ if African American})$ (SI units)

7. Pregnancy, lactation, or planned pregnancy during the course of the study and for 3 months after the final study visit.
8. Recent history (within past 12 months) of any unstable psychiatric disease (or any yes response to questions 1 or 2 on the Columbia–Suicide Severity Rating Scale [C-SSRS] at Screening), or current signs and symptoms of significant medical disorders such as severe, progressive, or uncontrolled pulmonary, cardiac, [REDACTED] hepatic, renal, genitourinary, hematological, endocrine, immunologic, or neurological disease.
9. History of epilepsy.
10. Current significant cognitive deficit, severe or untreated anxiety, severe or untreated depression.
11. Subjects with abnormal micturition that requires indwelling or intermittent catheterization or with lower urinary tract symptoms (LUTS) that result in a score >26 in the Visit 2 (Baseline) Urinary Symptom Profile – USP[®] (USP) questionnaire (Appendix 7). Subjects who are proficient in self-catheterization may be included in the study at investigator discretion.
12. Subject has clinically significant abnormal laboratory values, in the opinion of the investigator, at Visit 1 (Screening).

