7.7 Prior and Concomitant Therapy

The inclusion and exclusion criteria ([Section 5.1](#) and [Section 5.2](#), respectively) provide details on prohibited medications and the permitted duration since their last use prior to Screening and/or study drug administration. All medications taken within 90 days before Visit 2/Baseline (randomization) are to be recorded in the CRF/eCRF. Eligible patients will undergo up to a 21-day washout period (no drug onboard) for withdrawal of all medications used for anti-spasticity and/or muscle relaxation prior to randomization (see Inclusion Criterion 6). Subjects will be ineligible for randomization if they concomitantly use any of the medications listed in Appendix 6 (see Exclusion Criterion 5). Table 3 presents the half-life, taper period, and washout period for specific anti-spasticity and/or muscle relaxation medications. Tapering of an existing anti-spasticity drug depends on the dose of the drug and other conditions. The investigator should use medical judgment to safely taper the dose. Under most conditions, the taper should take no more than 2 weeks. For anti-spasticity medications not shown in Table 3, please contact the medical monitor for discussions of the washout period.

Table 3: Taper and Washout Periods for Specific Anti-spasticity and/or Muscle Relaxation Medications, Study OS440-3004

Drug	Half-Life (hours)	Taper Period	Washout Period
Baclofen	3 to 5	3 to 14 days	1 day
Clonidine	12 to 16	3 to 14 days	3 days
Dantrolene	8 to 9	3 to 14 days	2 days
Gabapentin	5 to 7	3 to 14 days	2 days
Zanaflex	3	3 to 14 days	1 day
Diazepam	100	3 to 14 days	3 weeks

All conventional medications regularly used for the treatment of MS, other than anti-spasticity medications, and non-pharmacological therapies (intended to alleviate spasticity, eg, physiotherapy) are allowed provided they have been taken/administered for at least 1 month prior to enrollment and no dose adjustments are expected for the duration of this study.

Changes in either the dose or frequency of concomitant medications taken for the treatment of MS should not be made for the duration of this study. In the event a dose adjustment is needed for a concomitant medication, the Investigator will contact the Sponsor to determine if the subject may remain in the study or needs to be withdrawn.

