Appendix 6. Prohibited Concomitant Medication List

[figure not shown]
- Aminoglycoside antibiotics
- Baclofen
- Benzodiazepines
- Botulinum toxin therapy of any serotype
- Cannabinoids
- Carisoprodol
- Chlormezanone
- Curariform drugs
- Dalfampridine
- Dantrolene
- Gabapentin for anti-spasticity indication
- Meprobamate
- Methocarbamol
- Neuroleptics such as tricyclic antidepressants and narcotics
- Orphenadrine
- Cyclobenzaprine
- Tizanidine
- Tolperisone

[figure not shown]

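### Dalfampridine: Inclusion 5 implies that stable users may enter, while Appendix 6, through Exclusion 5 and Section 7.7, bars them from randomisation

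*Protocol*

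**What the plan says.** Four places in the current protocol bear on the drug.

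- **Section 5.1, Inclusion 5**, after its sentence on disease-modifying drugs, turns to subjects receiving AMPYRA, names the substance and sets a condition: "subject must be at a stable dose for at least 3 months prior to Visit 1 (Screening".
- **Section 5.2, Exclusion 5** excludes "Concomitant use of medications that would potentially interfere with the actions of the study medication or outcome variables (Appendix 6". The section opens by saying that "Subjects who meet any of the following criteria will not qualify for the study".
- **Section 7.7** repeats the bar: "Subjects will be ineligible for randomization if they concomitantly use any of the medications listed in Appendix 6".
- **The list itself**, "Appendix 6. Prohibited Concomitant Medication List", has the entry "Dalfampridine" with nothing about dose, stability or indication.

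The SAP does not mention dalfampridine. It defines the PP population (SAP 7.1.4, as in Protocol 11.2) as subjects who finish study treatment without a significant deviation. SAP 8.2 leaves it to the sponsor's blinded review to decide which violations remove a subject from that population.

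**The concern.** A condition on the dose of a drug at entry tells a site that users of the drug can be entered. An unqualified place on the prohibited list, made binding by an exclusion criterion, tells the site that they cannot. A site that works from the inclusion list and a site that works from Appendix 6 would treat the same patient differently.

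Two things are at stake.

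- **Who is randomised.** The mix of dalfampridine users in the trial would depend on which part of the protocol a site relied on.
- **Who counts as a deviator.** A user who is randomised meets Inclusion 5 but also meets Exclusion 5. The blinded reviewers have no single rule to apply, and both co-primary analyses are to be repeated in the PP population (Protocol 11.4.1, SAP 9.1.3).

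The protocol gives its own reason for caring. Exclusion 5 describes the Appendix 6 drugs as able to interfere with the study drug's action or with the outcome variables, though it does not say which of the two applies to dalfampridine.

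**Working it through.** No arithmetic applies. The check applies each rule to one patient and then looks for text that would reconcile them. The patient has taken dalfampridine at an unchanged dose for at least 3 months before Visit 1 and goes on taking it.

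| Rule | Result for this patient |
|---|---|
| Inclusion 5 | Condition met |
| Appendix 6 | Drug is listed, no exception |
| Exclusion 5 | Exclusion met, through Appendix 6 |
| Section 7.7 | Not eligible for randomisation |

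**Step 1: the formal result.** Inclusion criteria are necessary conditions, and any one exclusion disqualifies. The patient is therefore ineligible. The AMPYRA sentence then does nothing, since every continuing user it could admit is removed by Exclusion 5.

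**Step 2: is there an exception for stable use?** None was found in either document. Appendix 6 can carry exceptions: its gabapentin entry is limited to use against spasticity. The dalfampridine entry has no such limit.

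**Step 3: could the drug be accepted at screening and stopped before Visit 2?** Baclofen follows that path. It is on Appendix 6, but Inclusion 6a accepts users at screening and requires washout, and Table 3 gives taper and washout times. For dalfampridine the corresponding text is absent:

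- Inclusion 6a covers drugs indicated for spasticity, and dalfampridine is not among its examples.
- Table 3 has no entry for it. The instruction to ask the medical monitor about drugs missing from Table 3 is confined to anti-spasticity drugs.
- Inclusion 5 places it beside the disease-modifying drugs, and Section 7.7 asks that MS medication not be changed in dose or frequency during the study.

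**Step 4: does Section 7.7 supply another rule?** It allows conventional MS medication, other than anti-spasticity drugs, if taken for at least 1 month before enrolment. A site that classed dalfampridine there would find a shorter period than the 3 months of Inclusion 5, and still no release from Appendix 6.

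**Step 5: where does it reach the analysis?** The efficacy population is ITT, meaning all randomised subjects analysed as randomised (Protocol 11.2, SAP 7.1.2). Eligibility is settled before allocation, so the conflict gives no mechanism for bias between arms in the primary comparison. It does reach PP membership, which depends on what counts as a significant deviation.

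**Step 6: size.** The number affected would be the share of users multiplied by the number of subjects. Protocol Section 5 plans about 510 randomised subjects, but neither document gives a share.

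**The case against.** The best case for the plan has four parts.

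1. **There is no strict impossibility.** Inclusion 5 restricts users; it does not expressly let them continue. A site that turns away every current user breaks no rule. This stands. A reader might infer that the two rules cannot both be obeyed, or that one patient is formally both eligible and ineligible. The documents do not support that, because the exclusion governs. What remains is a sentence with no function that invites the opposite reading.
2. **The rules may apply at different times.** Inclusion criteria are judged at Visit 1, while Section 7.7 speaks of randomisation at Visit 2. The disease-modifying sentence of Inclusion 5 asks for willingness to keep the dose throughout the study; the AMPYRA sentence does not. This is a fair textual point, but nothing in the protocol tells a site to stop the drug, for the reasons in Step 3.
3. **Sites have somewhere to ask.** Section 7.7 sends questions on medication to the Medical Monitor. This stands, so differing practice between sites is a risk and not a certainty. It helps only if a site sees that there is a question.
4. **The PP analyses are supportive, and removal is not automatic.** SAP 8.2 says that a major violation may lead to removal after blinded review. This also stands. It limits the consequence, but the reviewers still need one rule to judge by.

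A reader might also infer a count by applying a guessed share of users to the 510 planned subjects. The documents give no basis for the share. The product would also mix two situations: under Appendix 6 users are never randomised, and under Inclusion 5 they are not violators.

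**Conclusion.** The eligibility text is inconsistent on dalfampridine and needs correction. On a strict reading a continuing user is ineligible, and the AMPYRA sentence is without effect. On a reading that a site could reasonably adopt, a stable user may enter. Enrolment of users, and their status as deviators for the PP analyses, may therefore be inconsistent.

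The consequence is limited. The primary ITT comparison of either dose with placebo is not invalidated, and a reader who infers otherwise goes beyond the documents. The number of subjects concerned cannot be computed from them, and it could be small. The conclusion rests only on the wording of the four places and on the absence of any text that reconciles them. It takes no position on whether the drug should be allowed.

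**What to change.** - Reconcile Inclusion 5, Exclusion 5, Section 7.7 and Appendix 6 so that they state one rule on dalfampridine. Which rule it should be is for the sponsor to decide.
- Apply that rule to any users already randomised when the deviation file of SAP 8.2 is prepared, blinded and before database lock. That process is already planned; the only addition is an entry saying whether dalfampridine use at entry is a deviation and whether it removes a subject from PP.

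The cost is a short protocol amendment, which under Protocol 12.2 needs sponsor and IRB/IEC approval before it takes effect, and one entry in the deviation specification. Sample size, visits and primary models are unchanged.

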4 INVESTIGATIONAL PLAN

4.1 Overall Study Design

This is a multicenter, randomized, double-blind, placebo-controlled, parallel-group study to evaluate the safety and efficacy of oral AERT in MS patients with spasticity. Two doses of AERT, 40 mg and 80 mg, will be compared with placebo. The treatment groups will be randomized in a 1:1:1 ratio. There will be a 9-day titration period, then a 75-day maintenance period, followed by a 7-day taper period. Figure 1 presents the timeline diagram for the study. Figure 2 presents the blinded dosing regimen flowchart, including titration and taper doses, to be used during the study. The dosing schema is presented in Figure 3.

Eligible patients will undergo up to a 21-day washout period for withdrawal of all medications used for anti-spasticity and/or muscle relaxation prior to randomization. A baseline clinical evaluation will be performed (Visit 2) to confirm eligibility for study randomization, and subjects will be randomly assigned to 1 of 3 treatment arms: (1) AERT 40 mg; 2) AERT 80 mg; or 3) placebo. During the first 9 days of drug administration, doses will be titrated every 3 days to a fixed-dose of either AERT 40 mg, AERT 80 mg, or placebo. Subjects will remain at that fixed-dose for 75 days. The co-primary efficacy assessments, changes from baseline in the total numeric-transformed modified Ashworth Scale score of the most affected limb (TNmAS-MAL) and in the Clinical Global Impression of Change (CGIC), will be performed as shown in Table 1. At the end of the maintenance period, the subject's dose will be tapered for an additional 7 days before the subject returns to the site for a final safety evaluation at Day 92 (Visit 6). Table 1 describes the study visits and timing of all study procedures and assessments.

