- Record vital sign measurements, including blood pressure (BP), heart rate, respiratory rate, and body temperature ([Section 9.2](#)).
- Collect blood and urine samples for hematology, serum chemistry, and urinalysis ([Section 9.5](#)). Subject should be fasting if possible. As per Exclusion Criterion 12, if, in the opinion of the investigator, a subject has clinically significant abnormal laboratory value(s) at Visit 1 (Screening), they will be excluded from the study.
- Perform a standard 12-lead electrocardiogram (ECG) ([Section 9.6.1](#)).
- Collect a blood sample for serum pregnancy testing for women of childbearing potential. Because contraception is required throughout the study for both males and females, the use of an acceptable method throughout the study will be discussed with all subjects ([Section 7.8](#)).
- Administer the C-SSRS ([Section 9.6.3](#)).

- Administer the EDSS ([Section 8.4](#)).
- Administer the USP questionnaire ([Section 9.6.2](#)).
- Record all concomitant medications/therapies the subject is currently taking ([Section 7.7](#)).
- Schedule the next visit within approximately 7 to 14 days.

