7.8 Use of Contraception and Pregnancy Testing

Prior to study enrollment, females of childbearing potential and female partners of male subjects must be advised of the importance of avoiding pregnancy during study participation and the potential risk factors for an unintentional pregnancy. Females of childbearing potential include any female who has experienced menarche and who has not undergone successful surgical sterilization (hysterectomy, bilateral tubal ligation/occlusion, or bilateral oophorectomy) or is not postmenopausal (defined as amenorrhea >12 consecutive months). Premenopausal women of childbearing potential must have a negative serum pregnancy test within 21 days before Visit 2 (Baseline) and, if they are sexually active or become sexually active during the study, must use an effective method of birth control such as those listed below during the course of the study. Urine pregnancy testing will be done at Visits 2 through 6.

The following is not an all-inclusive list; the subject must discuss with the Investigator the most appropriate form of birth control:

- Hormonal methods
 - Oral contraceptives
 - Implant
 - Injection
 - Transdermal patch
 - Intravaginal ring
- Intrauterine device (hormonal or non-hormonal)
- Barrier methods
 - Condom (male or female) with spermicide
 - Diaphragm with spermicide
- Complete abstinence

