- **Other:** Other reasons include but are not limited to: Investigator decision that it is in the subject's best interest to be withdrawn, administrative reasons, relocation of subject, etc. If a subject or the partner of a subject becomes pregnant during the study, the subject will be withdrawn from the study and followed through conclusion of the pregnancy (see [Section 9.7.5](#)).

When possible, a decision to discontinue a subject from the study should first be discussed with the Sponsor's Medical Monitor. If a subject is prematurely discontinued after randomization and prior to the final scheduled visit, every effort should be made to perform all of the Visit 6 assessments (Table 1). The reason(s) for early withdrawal must be recorded in the CRF/eCRF. Subjects withdrawn from the study will not be replaced.

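### Inclusion 9 relies on Section 7.8 for its contraception rule, but Sections 7.8 and 6.1 state a different standard, population and duration, so the passages must be reconciled

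*Protocol*

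**What the plan says.** Four places in the protocol set or describe the contraception requirement.

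- **Section 5.1, criterion 9** asks for "Use of a medically highly effective form of birth control (see [Section 7.8](#)) during the study and for 3 months thereafter". It applies this to women of child-bearing potential, who are said to include both female subjects and the female partners of non-sterile men. A second sentence applies it to any subject whose partner is neither sterilized nor postmenopausal. Both sentences point to Section 7.8.
- **Section 7.8** says that premenopausal women of childbearing potential who are or become sexually active "must use an effective method of birth control such as those listed below during the course of the study". Before enrollment, "females of childbearing potential and female partners of male subjects must be advised of the importance of avoiding pregnancy during study participation". Its list of methods is introduced with "The following is not an all-inclusive list; the subject must discuss with the Investigator the most appropriate form of birth control".
- **Section 6.1 (Screening)** says: "Because contraception is required throughout the study for both males and females, the use of an acceptable method throughout the study will be discussed". Every subject is to have this discussion. The section also points to Section 7.8.
- **Section 5.2, criterion 7** excludes "Pregnancy, lactation, or planned pregnancy during the course of the study and for 3 months after the final study visit".

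Section 9.7.5 repeats the Section 7.8 advice about study participation and says the consent form must document that discussion. Its instruction on a suspected pregnancy covers the time before or during the study.

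**The concern.** A criterion that cites another section for its content should find that content there. Here the cited section differs from the criterion on three elements: how good the method must be, who must use it, and for how long. Section 6.1, the instruction for the visit at which contraception is discussed, gives a third version.

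The rule exists to prevent fetal exposure. Section 7.8 is the titled contraception section and both other passages point to it, so a site could reasonably take it as the full statement. A subject counselled from it would hear a shorter period and a differently worded standard than criterion 9 sets. Table 1 schedules nothing after Visit 6, so no later planned visit would correct the omission.

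**Working it through.** The plan states no figure to reproduce. The check is a comparison of text, with one small calculation for the length of the difference.

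**Step 1. The passages side by side**

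| Element | 5.1 criterion 9 | 7.8 | 6.1 | 5.2 criterion 7 |
|---|---|---|---|---|
| Standard | highly effective | effective | acceptable | not applicable |
| Who | female subjects; female partners of non-sterile men; any subject whose partner is not sterilized or postmenopausal | duty to use: premenopausal women of childbearing potential who are or become sexually active; female partners of men: to be advised | both sexes | any subject pregnant, lactating or planning pregnancy |
| Until | end of study plus 3 months | end of study | end of study | 3 months after the final visit |

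**Step 2. Does 7.8 supply what criterion 9 sends the reader there to find?**

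- *Standard.* No. The words highly effective do not occur in Section 7.8. The list is open and does not say which methods meet the higher term.
- *Population.* Not in full. The duty to use a method is placed only on sexually active premenopausal women. Partners of male subjects are to be advised, not required. The condition on sexual activity matters less in practice, because the list accepts complete abstinence.
- *Duration.* No. The 3 months are absent.

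**Step 3. Is the 3-month period intended?** Yes, on the documents. Criterion 7 in Section 5.2 carries the same length, anchored to the final study visit.

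**Step 4. Length of the difference**

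- Input: "final safety evaluation at Day 92 (Visit 6"), from Section 4.1.
- Assumption: 3 months is 90 to 92 days. The protocol does not convert it.
- Criterion 9 runs to 92 + 90 = Day 182 up to 92 + 92 = Day 184, so about Day 183.
- Section 7.8 runs to the end of the study, nominal Day 92.
- Difference: 183 − 92 = 91 days. Section 7.8 therefore spells out 92/183 = 0.50 of the period in criterion 9.
- Visit 6 has a window of ±5 days (Day 87 to 97). This moves both end points together, so the difference stays at 3 months. The same holds for a subject who terminates early, if the early termination visit is taken as the end of that subject's study.

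**The case against.** The strongest reply is that criterion 9 governs enrollment whatever Section 7.8 says. Sections 6.1 and 6.2 have the site assess eligibility against 5.1 and 5.2 at Visits 1 and 2. Section 7.4 requires staff to acknowledge that every inclusion criterion is met before an enrollment number is given. A subject who satisfies only Section 7.8 has not satisfied criterion 9. The consent pages are not in the public text and may state the 3 months. All of this stands, and it limits the consequence. It does not remove the contradiction, because criterion 9 itself relies on Section 7.8.

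Several stronger readings are tempting, and the documents do not support them.

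- *Subjects will stop contraception 3 months early.* Section 7.8 is silent after the study and tells no one to stop. The shortfall arises only where a site works from 6.1 or 7.8 alone.
- *The list in 7.8 falls short because it includes barrier methods.* The protocol never ranks methods or defines highly effective. Given the cross-reference, the list could be read as its own definition.
- *Men carry no duty.* Section 6.1 says contraception is required of both sexes during the study. The gap is in Section 7.8, and between the passages.
- *Pregnancies in the 3 months have no reporting route for a countable number of days.* One could run the 30-day adverse event pick-up in Section 9.7.3 to Day 122 and count 183 − 122 = 61 days left over. But Section 9.7.5 says pregnancy is not captured as an adverse event, so that count has no basis. Part of Section 9.7.3 and the safety reporting appendix are redacted, so the absence of a route cannot be confirmed.
- *Section 12.4 should reach into the 3 months.* Its wording, "If a subject or the partner of a subject becomes pregnant during the study", governs withdrawal, and a subject who has completed Visit 6 can no longer be withdrawn.

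**Conclusion.** The contradiction is real and is in the current text. Criterion 9 and the section it cites disagree on method standard, population and duration, and Section 6.1 adds a third wording. In time, the difference is the 3 months after the final visit, nominally Day 92 to about Day 183. This assumes the nominal visit day and 90 to 92 days for 3 months. The practical effect depends on whether a site counsels from 6.1 or 7.8 without going back to 5.1 and 5.2, and the documents do not show how often that would happen.

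This is an inconsistency in safety text. It has no bearing on endpoints, sample size, power or type I error. It is more than clerical because the passages are instructions that sites act on. It should be corrected, but it does not put the trial's conclusions at risk.

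**What to change.** Reconcile Section 5.1 criterion 9, Section 5.2 criterion 7, Section 6.1 and Section 7.8 so that they state one method standard, one population (female subjects, male subjects and partners, as decided) and one end date. Then check that the pregnancy counselling and reporting text in Section 9.7.5 agrees with the end date chosen, and that the consent form says the same. Which standard, population and end date should stand is for the sponsor to decide; this point does not propose one.

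The cost is protocol wording, a check of the consent form, and the ethics committee approval that Section 12.2 requires for any amendment. Aligning the text does not in itself add a visit, change data collection or alter the SAP.
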